13.4.2. Treatment State

Within each treatment study phase (i.e. Maintenance and Extension—based on assignment of study phase described in Section 13.4.1), only those assessments which occur within the ranges shown in Table 20 will be considered ‘on-treatment’ for the given phase.

Table 20 Treatment State within Study Phases

Study Phase	Treatment State	Date Range
Screen	Pre-treatment	All assessments/events within phase
Maintenance	On-treatment	Current ART arm: Date \leq Maintenance Current ART Stop Date + 1
		IM Q4W arm: Date \leq max(Date of Last Q4W IM Dose + 35, Last Oral dose Date + 1);
	Post-treatment	Current ART arm: Date $>$ Current ART Stop Date + 1
		IM Q4W arm: Date $>$ max(Date of Last Q4W IM Dose + 35, Last Oral dose Date + 1)
Extension	On-treatment	Date \leq max(Date of Last Q4W IM Dose + 35, Last Oral dose Date + 1)
	Post-treatment	Date $>$ Date of Last Q4W IM Dose + 35, Last Oral dose Date + 1)
Long-Term Follow-up	On-treatment	Date \leq min(LTFU ART start date, max(Last Injection Date + 35, Last Oral dose Date + 1))
	Post-treatment	Date $>$ min(LTFU ART start date, max(Last Injection Date + 35, Last Oral dose Date + 1))

Note1: Treatment State is determined after data has been assigned to the study phases as defined in Section 13.4.1

Note2: Last Q4W IM / last oral dose/ Maintenance Current ART Stop Date is only applied to subjects who permanently discontinue from study treatment

Note3: Date = Assessment/Start Date.

13.4.2.1. Treatment States for AE Data

For adverse events, partial AE start date will use imputation as described in Section 13.7.2.1. In the case of a completely missing start date, the event will be considered to have started On-treatment at Maintenance phase unless an end date for the AE is provided which is before start of study treatment at Maintenance phase; in such a case the AE is assigned as Pre-treatment.

Within each treatment study phase, only those AE with onset date within the ranges shown in Table 20 will be considered 'on-treatment' for the given phase. The onset date will be derived Based on Table 18.

Table 21 AE onset date, AE duration and relation to study treatment

	Definition
Onset date/study day Since 1 st Dose of each study phase (Days)	If Treatment Start Date > AE Onset Date = AE Onset Date - Treatment Start Date If Treatment Start Date ≤ AE Onset Date = AE Onset Date - Treatment Start Date + 1 Missing otherwise.
Duration (Days)	AE Resolution Date – AE Onset Date + 1
Drug-related	If relationship is marked 'YES' on Inform/CRF OR value is missing.

NOTES:

- Onset date/study day will be derived for each study phase, respectively (refer to Section [13.6.1](#))

13.4.3. Combining Treatment Phases and States

On-treatment and Post-treatment assessments and events will be classified as occurring during the Maintenance Phase, Extension, or Long-term follow up phase.

13.5. Appendix 5: Data Display Standards & Handling Conventions

13.5.1. Reporting Process

Software	

 The currently supported versions of SAS software will be used. 	
Reporting Area	
HARP Server	: uk1salx00259
HARP Area	: \ARPROD\GSK1265744\mid201585\week48 : \ARPROD\GSK1265744\mid201585\idmc_01
QC Spreadsheet	: \ARWORK\GSK1265744\mid201585\documents\qc\TBD
Analysis Datasets	

 Analysis datasets for Week 48, 96 will be created according to CDISC standards (SDTM IG Version 3.1.3 & AdAM IG Version 1.0). For creation of ADaM datasets (ADCM/ADAE), the same version of dictionary datasets will be implemented for conversion from SI to SDTM. 	
Generation of RTF Files	

 RTF files will be generated for every reporting effort described in the RAP. 	

13.5.2. Reporting Standards

General	

 The current GSK Integrated Data Standards Library (IDSL) will be applied for reporting, unless otherwise stated (IDSL Standards Location: https://spope.gsk.com/sites/IDSLLibrary/SitePages/Home.aspx): 
 4.03 to 4.23: General Principles 5.01 to 5.08: Principles Related to Data Listings 6.01 to 6.11: Principles Related to Summary Tables 7.01 to 7.13: Principles Related to Graphics 	
Formats	

 GSK IDSL Statistical Principles (5.03 & 6.06.3) for decimal places (DP's) will be adopted for reporting of data based on the raw data collected, unless otherwise stated. Numeric data will be reported at the precision collected on the eCRF. The reported precision from non eCRF sources will follow the IDSL statistical principles but may be adjusted to a clinically interpretable number of DP's. 	
Planned and Actual Time	

 Reporting for tables, figures and formal statistical analyses: 
 Planned time relative to dosing will be used in figures, summaries, statistical analyses and calculation of any derived parameters, unless otherwise stated. The impact of any major deviation from the planned assessment times and/or scheduled visit days on the analyses and interpretation of the results will be assessed as appropriate. Reporting for Data Listings: 
 Planned and actual time relative to study drug dosing will be shown in listings (Refer to IDSL Statistical Principle 5.05.1). Unscheduled or unplanned readings will be presented within the subject's listings. 	

Unscheduled Visits	

 • Unscheduled visits will be assigned to a study visit using the all-inclusive windows defined in Section 13.3.2. • However, data summaries will only report visits that are planned assessment time points for each parameter (according to the Time and Events table). • Assessments at unscheduled visits will be included for 'any time On-treatment' time points and in data listings, as well any algorithms that make use of additional data (e.g., Snapshot). 	
Descriptive Summary Statistics	
Continuous Data	Refer to IDSL Statistical Principle 6.06.1
Categorical Data	N, n, frequency, %
Graphical Displays	

 • Refer to IDSL Statistical Principals 7.01 to 7.13. 	

13.5.3. Reporting Standards for Pharmacokinetic

Reporting of Pharmacokinetic Concentration Data	
Descriptive Summary Statistics	Refer to IDSL Statistical Principle 6.06.1 Assign zero to NQ values (Refer to GUI_51487 for further details)
Reporting of Pharmacokinetic Parameters	
Descriptive Summary Statistics (Log Transformed)	
N, n, geometric mean, 95% CI of geometric mean, standard deviation (SD) of logged data and between geometric coefficient of variation (CV_b (%)) will be reported.
 
 ○ $CV_b (\%) = \sqrt{(\exp(SD^2) - 1)} * 100$ (SD = SD of log transformed data)

13.6. Appendix 6: Derived and Transformed Data

13.6.1. General

Multiple Measurements at One Time Point

- If after window assignment there are multiple valid assessments of a parameter within the same window, then the following hierarchy will be used to determine the value to be used for summary statistics of observed values:
 - the assessment closest to the window target Study Day;
 - if there are multiple assessments equidistant from the target Study Day, then for continuous variables the mean of these values will be used and for categorical variables the worse assessment. For HIV-1 RNA, the geometric mean of the number of copies will be used as opposed to the arithmetic mean
- Assessments not chosen for use in summary statistics by this algorithm will still appear in the associated listings. Also, such valid assessments will be used when determining values of potential clinical concern for the 'any time On-treatment' time point, and for any algorithm that has specific rules for which observation to use (e.g., Snapshot).

Treatment Start Date

Treatment start date is defined as follows:
 
Maintenance Phase
 
 • For subjects randomised to Q4W IM, treatment start date is the date of oral lead-in of CAB+RPV entered onto the IP exposure CRF form when study treatment started. • For subjects randomised to Current ART, treatment start date is the date of the Day 1 visit. 
Extension Phase
 
 • For subjects randomised to Q4W IM, treatment start date is the date of Nominal Week 52 injection date. • For subjects randomised to Current ART, treatment start date is the start date of oral lead-in of CAB+RPV at Extension phase.
Study Day

The Study Day of an event (e.g., lab assessment, vital sign, ECG, start date of AE or HIV associated condition) will be derived as the number of days between the date of the event and the start date of study treatment on Maintenance phase as follows:
 
if date of event \geq start date of study treatment, then
 
 • Study Day = date of event - start date of treatment on Maintenance phase + 1 
if date of event < start date of study treatment, then
 
 • Study Day = date of event - start date of treatment on Maintenance phase 
Note that the start date of study treatment on Maintenance phase is considered to be on Study Day 1 and the day before this is Study Day -1; i.e., there is no Study Day 0.

Extension Phase Study Day

The Extension Phase Study Day of an event (e.g., lab assessment, vital sign, ECG, start date of AE or HIV associated condition) will be derived as the number of days between the date of the event and the initial start date of Extension phase IP as follows:
 
if date of event \geq start date of extension phase IP, then
 $\text{Extension Phase Study Day} = \text{date of event} - \text{start date of Extension phase IP} + 1$ 
if date of event < start date of Extension Phase IP, then
 $\text{Extension Phase Study Day} = \text{date of event} - \text{start date of Extension phase IP}$ 
Note that the start date of Extension phase IP is considered to be on Extension Phase Study Day 1 and the day before this is Extension Phase Study Day -1; i.e., there is no Extension Phase Study Day 0.

Long-Term Follow Up Study Day
The Long-Term Follow Up (LTFU) Study Day of an event (e.g., lab assessment, start date of AE or HIV associated condition) will be derived as the number of days between the date of the event and the end of IP treatment [i.e. $\max(\text{Last IM Injection Date}, \text{Last Oral Bridging End Date})$] as follows: If the onset of event falls in Long-term Follow up phase, then 
 • LTFU Study Day = date of event - end date of IP
Post-baseline

 • Post-baseline refers to the combined time phases of On-treatment and Post-treatment. Post-baseline may be further specified according to phase(s) of the study: Maintenance and Extension (for example, post-baseline across the maintenance and extension phases combined).
Study treatment/drugs

 • Refers to either investigation product (CAB+RPV oral /CAB+ RPV LA) or Current ARTs

13.6.2. Study Population

Demographics
Age

 • Age, in whole years, will be calculated with respect to the subject's Screening visit. • GSK standard IDSL algorithms will be used for calculating age where birth date will be imputed as follows: 
 ○ Any subject with a missing date and month will have this imputed as '30th June'. • Birth date will be presented in listings as 'YYYY'. • Completely missing dates of birth will remain as missing, with no imputation applied. Consequently, the age of the subject will not be calculated and will remain missing.
Body Mass Index (BMI)

 • Calculated as $\text{Weight (kg)} / \text{Height (m)}^2$
Hepatitis Status

 • Hepatitis C status will be determined using antibody (IgM or IgG) and/or hepatitis C virus (HCV) RNA assessments performed during screening or during the conduct of the study. • If both antibody and virus RNA assessments are available, then the latter will take precedence and positive/negative status will be based on whether HCV RNA is detectable (i.e., ≥ 43 IU/mL [≥ 1.63 log IU/mL]) or not. • A subject will be considered positive for hepatitis B virus (HBV) if they have a positive surface antigen or detectable HBV DNA result during screening. Subjects positive for HBV are not allowed to enter the study.
Lipid-modifying Agents

 • The following ATC codes correspond to lipid-modifying agents:

Demographics																							

 ○ ATC Level 2: C10 ○ ATC Level 3: C10A, C10B (if Level 2 is not available) ○ ATC Level 4: C10AA, C10AB, C10AC, C10AD, C10AX, C10BA, C10BX (if level 2, 3 are not available) 
 ● Subjects are considered to have used a lipid-modifying agent at baseline if they are taking the medication at the time of their baseline lipid testing date. 
Subjects are also considered to have used a lipid-modifying agent at baseline if they stopped their lipid modifying medication within 12 weeks prior to their baseline lipid testing date.
																							
Torsade des Pointes (TdP)																							

TdP cases will be identified based on Standardised MedDRA Query (SMQ) for Torsade de pointes/QT prolongation, broad (MedDRA). The terms per this reference are listed below.
 
  
 AE preferred term	
   
Electrocardiogram QT interval abnormal	
 
Electrocardiogram QT prolonged	
 
Long QT syndrome	
 
Long QT syndrome congenital	
 
Torsade de pointes	
 
Ventricular tachycardia	
 
Cardiac arrest	
 
Cardiac death	
 
Cardiac fibrillation	
 
Cardio-respiratory arrest	
 
Electrocardiogram repolarisation abnormality	
 
Electrocardiogram U wave inversion	
 
Electrocardiogram U wave present	
 
Electrocardiogram U-wave abnormality	
 
Loss of consciousness	
 
Sudden cardiac death	
 
Sudden death	
 
Syncope	
 
Ventricular arrhythmia	
 
Ventricular fibrillation	
 
Ventricular flutter	
 
Ventricular tachyarrhythmia	
  
	AE preferred term	Electrocardiogram QT interval abnormal	Electrocardiogram QT prolonged	Long QT syndrome	Long QT syndrome congenital	Torsade de pointes	Ventricular tachycardia	Cardiac arrest	Cardiac death	Cardiac fibrillation	Cardio-respiratory arrest	Electrocardiogram repolarisation abnormality	Electrocardiogram U wave inversion	Electrocardiogram U wave present	Electrocardiogram U-wave abnormality	Loss of consciousness	Sudden cardiac death	Sudden death	Syncope	Ventricular arrhythmia	Ventricular fibrillation	Ventricular flutter	Ventricular tachyarrhythmia
AE preferred term																							
Electrocardiogram QT interval abnormal																							
Electrocardiogram QT prolonged																							
Long QT syndrome																							
Long QT syndrome congenital																							
Torsade de pointes																							
Ventricular tachycardia																							
Cardiac arrest																							
Cardiac death																							
Cardiac fibrillation																							
Cardio-respiratory arrest																							
Electrocardiogram repolarisation abnormality																							
Electrocardiogram U wave inversion																							
Electrocardiogram U wave present																							
Electrocardiogram U-wave abnormality																							
Loss of consciousness																							
Sudden cardiac death																							
Sudden death																							
Syncope																							
Ventricular arrhythmia																							
Ventricular fibrillation																							
Ventricular flutter																							
Ventricular tachyarrhythmia																							

Demographics

Framingham Risk Equation

- The predicted probability, \hat{p} , of having a cardiovascular disease (CVD) within the next 10-years according to the Framingham formula [D’Agostino, 2008] is

for females:

$$\hat{p}_F = 1 - S_0(t)^{\exp\{ 2.32888 \times \log(\text{age}) + 1.20904 \times \log(\text{TC}) - 0.70833 \times \log(\text{HDL}) + 2.76157 \times \log(\text{SBPu}) + 2.82263 \times \log(\text{SBPt}) + 0.52873 \times I_s + 0.69154 \times I_d - 26.1931\}}$$

for males:

$$\hat{p}_M = 1 - S_0(t)^{\exp\{ 3.06117 \times \log(\text{age}) + 1.12370 \times \log(\text{TC}) - 0.93263 \times \log(\text{HDL}) + 1.93303 \times \log(\text{SBPu}) + 1.99881 \times \log(\text{SBPt}) + 0.65451 \times I_s + 0.57367 \times I_d - 23.9802\}}$$

where

$$S_0(t) = \{0.9501\text{-females, } 0.88936\text{-males}\}$$

TC = total serum cholesterol (mg/dL),

HDL = serum HDL cholesterol (mg/dL),

SBPu = systolic blood pressure (mmHg) if subject is not treated for high blood pressure (note that if a subject is treated for high blood pressure then $\log(\text{SBPu}) = 0$)

SBPt = systolic blood pressure (mmHg) if subject is treated for high blood pressure (note that if a subject is not treated for high blood pressure then $\log(\text{SBPt}) = 0$)

$$I_s = \begin{cases} 1, & \text{current smoker} \\ 0, & \text{otherwise} \end{cases}$$

$$I_d = \begin{cases} 1, & \text{diabetic} \\ 0, & \text{otherwise} \end{cases}$$

- A subject will be considered as treated for high blood pressure if during screening it has specified that is suffering from hypertension.
- A subject is classified as diabetic if current or past is indicated in the medical conditions eCRF for Type 1 or Type 2 diabetes mellitus, or if baseline fasting glucose ≥ 7.00 mmol/L (126 mg/dL).
- Smoking status is collected in the eCRF on Day 1. A current smoker is defined as currently smoking/using tobacco or has smoked/used tobacco within the previous 6 months; a former smoker is defined as previously smoked/used tobacco products and has not smoked/used tobacco products within the previous 6 months.
- This calculation will not be performed for subjects who have indicated current or past myocardial infarction conditions on the eCRF. These subjects will not be included in summary statistics of risk, but will be counted in the highest category of risk in the summary by category.

Extent of Exposure

- Exposure to CAB+RPV (oral lead-in) and CAB LA+RPV LA will be calculated from the IP eCRF pages. Exposure to Current ART will be calculated from the CONART eCRF pages.

Q4W IM arm:

- For Maintenance Phase:
 - Exposure to CAB + RPV (oral lead-in) = IP (oral lead-in) stop date- IP (oral lead-in) start date +1
 - Exposure to CAB LA + RPV LA = Number of IP injections received during Maintenance Phase
 - Overall exposure to IP = min [Date of nominal Week 52 visit, max(Date of last IP injection +35, date of last oral CAB/RPV)] - Oral lead-in CAB/RPV Start Date +1
- For Maintenance + Extension Phase
 - Exposure to CAB LA + RPV LA = Number of IP injections received during Maintenance Phase + Extension Phase
 - Overall Exposure to IP = (Date of last IP injection +35, - Oral CAB/RPV Start Date +1

Current ART arm

- For Maintenance Phase:
 - If a subject continues to Extension phase
Exposure = (IP Start Date at extension phase – 1) – Day 1 DOV + 1
 - If a subject discontinues prior to Nominal Week 52,
Exposure = Min (Current ART stop date, withdrawal date) – Day 1 DOV + 1
 - If a subject chooses to complete the study participation at Nominal Week 52 and not to continue to Extension phase, then
Exposure=completion date – Day 1 DOV +1

Current ART stop date is the last permanently stop date among all ARTs taken during Maintenance phase.

- For Extension Phase (Extension Switch Population only):
 - Exposure to CAB + RPV (oral lead-in) = IP (oral lead-in) stop date- IP (oral lead-in) start date +1
 - Exposure to CAB LA+ RPV LA = Number of IP injections received during Extension Phase
 - Overall exposure to IP = max(Date of last IP injection+35, date of last oral CAP/RPV) - Oral CAB/RPV lead-in Start Date +1
- Duration of dosing in subject years will be calculated as the sum of subject duration of dosing in days (across all subjects)/365.25
- Subjects who were randomised to CAB LA+RPV LA but did not report a IP start date will be categorised as having zero days of exposure.
- Subjects who were randomised to Current ART but withdrew on Day1 will be categorised as having zero days of exposure.
- For Current ART arm, missing IP discontinuation Date will be imputed, for purposes of calculating exposure, as the date of last visit or the recorded date of withdrawal/completion, whichever is earlier.

Adherence to CAB/RPV Injection Schedule

Timeliness of Injections Relative to Date of Projected Dosing Visits are assessed by using "actual injection visit date - projected visit date from Week 4B". Each injection visit is counted only once. Individual CAB and RPV injections administered at the same visit are not counted twice. "Extra" unscheduled injections are excluded from all derivations. For example, if during a scheduled visit a subject receives 1 ml of injection instead of 2 ml due to a dosing error, but returns one week later for the remaining 1 ml injection, then the additional visit is excluded. If a subject receives an extra injection at an unscheduled visit by mistake, this visit will also be excluded.

The categories of Timeliness of Injections Relative to Date of Projected Dosing Visits for summary are listed below:

- < -14 days
- 14 to - 8 days
- 7 to - 4 days
- 3 to -2 days -1
- 0 day
- 1
- 2 to 3 days
- 4 to 7 days
- 8 to 14 days
- >14 days
- Missed Injection without Oral Bridging
- Missed Injection with Oral Bridging

Corrected QTC

When not entered directly in the eCRF, corrected QT intervals by Bazett's (QTcB) and Fridericia's (QTcF) formulas will be calculated, in msec, depending on the availability of other measurements.

If RR interval (in msec) is provided then missing QTcB and/or QTcF will be derived as

$$QTcB = \frac{QT}{\sqrt{RR/1000}} \qquad QTcF = \frac{QT}{\sqrt[3]{RR/1000}}$$

where uncorrected QT interval is also measured in msec.

If RR interval is not provided directly and one of QTcB or QTcF has been entered, then RR interval can be obtained from the above formulas and used to calculate the other correction method value; i.e.,

$$QTcB = \sqrt{\frac{QTcF^3}{QT}} \qquad QTcF = \sqrt[3]{QT \cdot QTcB^2}$$

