6. STUDY POPULATION ANALYSES

6.1. Overview of Planned Study Population Analyses

The study population analyses will be based on the Intent-to-Treat Exposed population, unless otherwise specified.

Study population analyses including analyses of subject's disposition, protocol deviations, demographic and baseline characteristics, prior and concomitant medications, and exposure and treatment compliance will be based on GSK Core Data Standards. Details of the planned displays are presented in [Appendix 13: List of Data Displays](#).

[Table 2](#) provides an overview of the planned study population analyses, with full details of data displays being presented in [Section 13.13: List of Data Displays](#).

Table 2 Overview of Planned Study Population Analyses

Display Type	Data Displays Generated	
	Table	Listing
Randomisation		
Randomisation ^[1]		Y ^[2]
Subject Disposition		
Study Populations ^[3]	Y	Y ^[4]
Study Recruitment ^[3]	Y	Y
Reasons for Screening Failures ^[3]	Y	Y
History of Rescreened Subjects ^[3]		Y
Age categories	Y	
Subject Disposition	Y ^{[5][6]}	
Reasons for Withdrawal by Visit	Y ^{[5][6]}	Y
IP discontinuation	Y	Y
Important Protocol Deviations	Y	Y
Deviations leading to exclusion from PP	Y	Y
Inclusion and Exclusion Criteria Deviations	Y	Y
Demography and Baseline		
Demographics Characteristics ^[7]	Y	Y
Race & Racial Combinations ^[8]	Y	Y
Hepatitis Status	Y	Y
CDC Classification of HIV infection (2014)	Y	Y
Cardiovascular Risk Assessments at Baseline	Y	Y
Distribution of CD4+ Cell Counts	Y	
History of Cardiac Therapeutic Procedures		Y

Display Type	Data Displays Generated	
	Table	Listing
Medical Conditions, Concomitant Medications & Antiretroviral Therapy		
Medical Conditions (Current/Past) ^[9]	Y	Y
Medical Conditions: Sub-conditions (Current/Past) ^[9, 10]	Y	
Concomitant Medications (non-ART)	Y ^[11]	Y ^[12]
Antiretroviral Therapy stopped Prior to Screening ^[13]	Y	Y ^[14]
Antiretroviral Therapy Taken during Screening	Y	Y ^[15]
Antiretroviral Therapy Taken Prior to & during Screening for Subjects Failing ART Eligibility Criteria		Y
Concomitant Antiretroviral Therapy at Maintenance Phase	Y	Y ^[15]
Baseline third agent class (Strata) ^[16]	Y	Y
Lipid Modifying agents (Baseline and Post-Baseline)	Y	
Substance use	Y	Y
Other		
Study Treatment Accountability ^[17]		Y

NOTES:

- T = Tables, L = Listings, Y = Display Generated,
1. All Participants Randomized population

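### The Framingham score in SAP section 13.6.2 uses a reported hypertension diagnosis as a stand-in for blood-pressure treatment, so some participants get the wrong systolic pressure coefficient

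*SAP*

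**What the plan says.** The Framingham Risk Equation entry in SAP section 13.6.2 prints one equation per sex. Each has two systolic pressure terms, and a participant contributes to only one of them:

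- "SBPu = systolic blood pressure (mmHg) if subject is not treated for high blood pressure"; its logarithm is set to 0 for treated participants.
- "SBPt = systolic blood pressure (mmHg) if subject is treated for high blood pressure"; its logarithm is set to 0 for untreated participants.

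Below the equations, the SAP states how the switch is set: "A subject will be considered as treated for high blood pressure if during screening it has specified that is suffering from hypertension". The entry does not mention antihypertensive medication, and it does not describe the rule as an approximation.

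The score feeds table 1.21 (section 13.13.4), the baseline cardiovascular risk table, due at Week 48, Week 96 and end of study. Section 13.6.2 indicates that risk is reported both as summary statistics and by category.

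Two other places bear on the remedy. Table 2 in section 6.1 plans a table and listings of non-ART concomitant medication. Section 13.6.2, shortly before the Framingham entry, derives baseline use of lipid-modifying agents from ATC codes and medication timing.

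**The concern.** The two pressure terms are separated by treatment, and the switch between them is driven by diagnosis. These are different facts about a participant. Someone with hypertension and no antihypertensive drug belongs in the untreated term by the variable definition but is placed in the treated term by the rule. Someone taking an antihypertensive for blood pressure who did not report hypertension is misplaced in the opposite direction.

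What is at stake is the accuracy of individual predicted risks, and hence of the summary in table 1.21. The treated coefficient is the larger one in both sexes, so each misplacement has a known direction and a size that can be calculated.

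**Working it through.** The SAP gives no figure for this effect, so there is none to reproduce. The check uses the printed coefficients.

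**Inputs from section 13.6.2**

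| | Women | Men |
|---|---|---|
| Coefficient, log untreated SBP | 2.76157 | 1.93303 |
| Coefficient, log treated SBP | 2.82263 | 1.99881 |
| Difference | 0.06106 | 0.06578 |
| Baseline survival | 0.9501 | 0.88936 |

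**Assumed input.** The SAP gives no distribution of systolic pressure, so 120 to 180 mmHg is used.

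**Step 1: effect on the hazard term.** Predicted risk is 1 − S0^exp(L), where L is the linear predictor. Moving one person from the untreated to the treated term changes L by (difference in coefficients) × ln(SBP). Everything else in L cancels, so exp(L) is multiplied by SBP^0.06106 in women and SBP^0.06578 in men.

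| Assumed SBP | Women | Men |
|---|---|---|
| 120 | 1.340 | 1.370 |
| 140 | 1.352 | 1.384 |
| 160 | 1.363 | 1.396 |
| 180 | 1.373 | 1.407 |

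The multiplier is thus 1.34 to 1.41 and varies little with the assumed pressure. For the opposite error the hazard term is divided by the same factor.

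**Step 2: effect on predicted 10-year risk.** Assumed profile: total cholesterol 200 mg/dL, HDL 45 mg/dL, non-smoker, non-diabetic.

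Man aged 50, SBP 145:
- Untreated term: L = 3.06117 ln 50 + 1.12370 ln 200 − 0.93263 ln 45 + 1.93303 ln 145 − 23.9802 = 0.019. exp(L) = 1.019. Risk = 1 − 0.88936^1.019 = 11.3%.
- Treated term: L rises by 0.06578 × ln 145 = 0.327. exp(L) = 1.414. Risk = 1 − 0.88936^1.414 = 15.3%.

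Other cases, calculated the same way:

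| Age, SBP | Sex | Untreated term | Treated term |
|---|---|---|---|
| 40, 140 | Man | 5.5% | 7.5% |
| 40, 140 | Woman | 3.9% | 5.3% |
| 50, 145 | Man | 11.3% | 15.3% |
| 50, 145 | Woman | 7.1% | 9.6% |
| 60, 150 | Man | 20.0% | 26.7% |
| 60, 150 | Woman | 11.7% | 15.6% |

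Per person, the shift in these examples is about 1.4 to 6.7 percentage points.

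**Step 3: effect on the cohort mean.** This needs the number misclassified, which the SAP does not give. As an illustration only, assume that 10% to 20% of participants report hypertension, that 10% to 30% of those are untreated, and that each gains about 4 points. Then 1% (0.10 × 0.10) to 6% (0.20 × 0.30) of the cohort is affected, and the mean moves by 0.04 to 0.24 points, before any offset from errors in the other direction.

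**The case against.** The strongest reply is that the rule is an explicit convention, fixed in advance. The variable definitions do not say how treatment is to be established; the later sentence does. Two programmers would code it identically. It uses screening information and applies the same way in both arms. The words also point to a screening entry on a form that is not shown. Section 13.2 schedules a cardiovascular risk assessment at Screening and Day 1, and that form might record treatment as well as diagnosis.

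Part of this stands. The derivation is reproducible, and it does not favour either arm. But a reproducible rule can still assign the wrong value, and as written this one turns on having hypertension, not on being treated for it. Nothing elsewhere in the SAP corrects it.

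A reader might infer three stronger things that the document does not support:

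- **That table 1.21 overstates risk by a third or more.** The multiplier applies to one misclassified person's hazard term. The effect on the table depends on how many such people there are.
- **That the net bias is upward.** Treated participants who did not report hypertension are scored too low, and the balance of the two errors is unknown.
- **That participants move into a higher risk category.** This is plausible, but no category cut-points are shown, so it cannot be verified.

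**Conclusion.** The point holds as a wrong derivation rule with a small consequence. Diagnosis stands in for treatment in a score whose variables are defined by treatment. For a hypertensive not on medication, the hazard term is inflated by a factor of 1.34 to 1.41 over an assumed systolic pressure of 120 to 180 mmHg. In the worked example at age 50, that is 4.0 points of 10-year risk in a man and 2.5 in a woman (15.3 − 11.3 and 9.6 − 7.1, with the profile stated above). A treated participant who did not report hypertension is understated by the same mechanism.

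The reach is limited to the descriptive baseline summary in table 1.21 and rests on an unknown number of misclassified participants. The score is not among the subgroups or covariates in section 5.4.2 and enters no endpoint or model, so efficacy results, treatment comparisons and type I error are untouched. This is a low-priority correction, worth making because it is cheap and changes reported numbers.

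**What to change.** Replace the diagnosis rule in section 13.6.2. A participant counts as treated for high blood pressure if concomitant medication records show an antihypertensive that is ongoing at baseline and taken for high blood pressure, whether or not hypertension was separately specified. Everyone else uses the untreated term.

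Requiring both a reported diagnosis and a drug would repair only one of the two errors: it would leave treated participants who did not report hypertension in the untreated term. The indication condition is needed because an antihypertensive may be taken for another reason.

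The wording can follow the lipid-modifying agent entry in the same section: an ATC list and a rule tying use to the baseline date. The cost is drawing up that list and one lookup in concomitant medication data that the SAP already plans to report.
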